6.1 Summary of Pre-Clinical and Clinical Testing (Prior Clinical Experience)

Pre-clinical testing for the Minitouch System demonstrates that the system performs as intended. Tests include the following in which the Minitouch System met the required pre-specified acceptance criteria:

- Design and Performance Verification
- Materials Testing (Biological Safety and Biocompatibility)
- Software
- Electrical Safety and EMC
- Usability
- Environmental & Life Cycle Testing
- Packaging/ Transportation Testing
- Sterilization Validation
- Dose Confirmation and Simulation Studies
- Ex-Vivo Human Uteri Ablation

The Minitouch System has been commercially available outside the United States (OUS) since 2011. As a result, there is extensive clinical experience with the device. Specifically:

- To date, there have been over 4000 real-world clinical procedures completed by more than 180 users at over 70 hospitals/centers predominantly located in the UK. Of these, one (1 or 0.025%) incidence of bowel injury occurred during clinical use. This event was attributed to procedural use errors and the patient was not an optimal candidate for the procedure.
- Additionally, there are over 50 publications (abstracts) reporting the OUS clinical experience of the Minitouch System. A safety analysis (review of all adverse events reported) was conducted.
 - A total sampling of 1,040 patients treated with the Minitouch System were included in the safety analysis.
 - A total of 14 events were reported in the literature and are summarized below. The events were consistent with those expected to occur in patients undergoing endometrial ablation.

| | Occurrence Rate |
|------------------------------------|-----------------|
| Event Description/Terminology | [n (%)] |
| (as reported in the literature) | (where N=1040) |
| Infection (suspected or confirmed) | 5 (0.48%) |
| Post-procedure pain/cramps | 7 (0.67%) |
| Vasovagal episode | 2 (0.19%) |

The Minitouch pre-clinical and clinical data are detailed in the Investigator's Brochure.

Page 20 of 65

CONFIDENTIAL & PROPRIETARY

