11.8.1 Reasons for Termination

Every patient should remain in the study until completion of the 36-month follow-up period. Whenever possible, an exit visit should be conducted to record reason(s) for withdrawal, retrieve study materials (PBLAC diaries) and complete relevant visit assessments such: AEs, concomitant medications, patient's menstrual status, NRS for dysmenorrhea-related pain and MIQ. Conceivable reasons for early patient discontinuation may include, but are not limited to, the following:

• Patient Withdrawal (voluntarily terminates consent): Patient participation in this clinical study is voluntary. The patient may choose to discontinue participation (refuse all subsequent testing) at any time without loss of benefits or penalty.

- **Discontinuation:** Patient participation may be discontinued by the patient or investigator because of a treatment modality change, organ transplant, transfer, death or prolonged hospitalization. The Sponsor may also decide to discontinue the testing of the study device.
- **Investigator-initiated Termination:** The Investigator may terminate the patient's participation without regard to the patient's consent if the Investigator believes it is medically necessary. In addition, the following circumstances may require early termination:
 - Patient is unable or unwilling to cooperate with study staff;
 - Emergence of clinically relevant serious adverse events, laboratory abnormalities or other medical condition or situation occurs such that continued participation would not be in the best interest of the patient;
 - Pregnancy
 - o Death
- Exclusion Criterion Discovered After Enrollment: A small number of patients may be enrolled despite meeting an exclusion criterion. This will be documented by the study personnel on the eCRF and will be considered a protocol deviation (PD), not termination.
- Lost-to-Follow-up: This category accounts for patients whose status is unclear because they fail to appear for study assessments/visits without stating intention to terminate consent. The data from this patient is still eligible for the intent-to-treat dataset. Site personnel should make all reasonable efforts to locate and communicate with the patient, at each contact time point, including:

A minimum of three (3) telephone calls to contact the patient should be attempted. Each attempt should be recorded in the patient's medical record, including date, time, and initials of site personnel attempting the contact.

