11.9 Point of Enrollment

A consented patient will be registered into the study EDC (eCRFs) and a unique subject identification number at the time of registration will be issued via the EDC. All data will be entered in the study EDC. If a patient later declines to participate, or is excluded from enrollment, the investigator will note the reason for non-participation in the study EDC.

A patient is considered enrolled when the following milestones have occurred: (1) the ICF is signed, (2) all applicable screening has been successfully completed, and (3) all study inclusion criteria and no exclusion criteria are met. Since the final selection criteria are re-assessed prior to procedure initiation on the date

of treatment (e.g.: pregnancy test, current medications, active infections) the patient may not be enrolled until that date. Specifically, final eligibility must be confirmed by the investigator prior to initiating the Minitouch procedure.

For additional clarity, a consented patient that does not proceed to treatment for any reason (such as screen failure, declines treatment or participation), is categorized as consented-enrolled. A qualified patient in whom the Minitouch procedure is initiated is categorized as treated-enrolled.

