17.1.1 Intent-to-Treat (ITT) Cohort

All patients who are enrolled in the study (enrollment defined as patients who met all study eligibility criteria and in whom the procedure is initiated) are included in the Intent-to-Treat (ITT) cohort.

The ITT cohort will be used for the following analyses (as defined in Section 9.1 & 9.2):

- Primary safety and effectiveness analyses at 12-month follow-up visits.
- Safety & effectiveness analyses at 24, and 36-month follow-up visits.

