20.2.2 Protocol Deviations

All protocol deviations will be classified as major or minor and documented and discussed in the Clinical Study Report.

A deviation is defined as any departure from clinical study requirements, including those cited within Good Clinical Practice (GCP) guidelines. Protocol deviations that affect the rights, safety, or welfare of human Patients must be reported to the study Sponsor as soon as possible from the occurrence of the deviation.

Major protocol deviations are defined as any protocol deviation that affects the soundness of the data or a Patient's rights. A major protocol deviation is non-compliance with the approved protocol and trial requirements that may impact patient safety, affect the integrity of the data and/or affect the patient's willingness to participate in the study.

Examples may include:

- Failure to meet all entry criteria;
- Non-compliant with device treatment regimen

A **minor** protocol deviation is non-compliance with the approved protocol and a trial requirement that does not impact Patient safety, compromise the integrity of the data and/or affect the Patient's willingness to participate in the study.

Protocol deviations must be reported to the IRB per the Institutional Review Board's reporting requirements. The occurrence of protocol deviations will be monitored by the study Sponsor and

Page 53 of 65

CONFIDENTIAL & PROPRIETARY

designee for evaluation of Investigator compliance to the study protocol, GCP guidelines, and regulatory requirements. Protocol deviations will be reviewed and evaluated by the study Sponsor or designee on an ongoing basis in accordance with the Protocol Deviation Management Plan, as applicable.

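### Sections 17.1.1 and 11.8.1 conflict on whether a treated woman later found ineligible is in the ITT cohort, so the denominator of both primary analyses is not fixed

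*Combined protocol and SAP*

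**What the plan says.** Section 17.1.1 puts two conditions on ITT membership through its definition of enrollment: "enrollment defined as patients who met all study eligibility criteria and in whom the procedure is initiated". The first use listed for the cohort is "Primary safety and effectiveness analyses at 12-month follow-up visits". Section 17.1.2 draws the PP cohort from ITT patients, so a woman outside ITT is outside PP too.

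Section 11.8.1 foresees that "A small number of patients may be enrolled despite meeting an exclusion criterion", and says that such a case "will be considered a protocol deviation (PD), not termination". It assigns her to no analysis cohort. The next bullet, on loss to follow-up, does: "The data from this patient is still eligible for the intent-to-treat dataset".

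Section 11.9 repeats the eligibility condition: "A qualified patient in whom the Minitouch procedure is initiated is categorized as treated-enrolled". Table 4-1 carries the same definition. Section 20.2.2 gives "Failure to meet all entry criteria" as an example of a major deviation and states no consequence for the analysis sets.

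**The concern.** The question is about women who were treated and whose ineligibility came to light afterwards, not women who were never treated. Under the literal wording of 17.1.1 such a woman is followed for 36 months but belongs to no analysis cohort. She also fits neither enrollment category in 11.9: she was treated, so she is not consented-enrolled, and she was not qualified, so she is not treated-enrolled.

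The trial is open-label and single-arm, and success is judged by one proportion against a fixed 66%. If cohort membership can be decided after the 12-month diary is in hand, the denominator can depend on the outcome. If the women set aside do worse than the rest, the success rate moves up against the OPC. The rule in 17.2 that missing data count as failures gives no protection, because it applies only inside ITT. The same cohort feeds the primary safety rate.

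**Working it through.** **Inputs.** From 17.2 and 17.2.1: null rate 0.66, expected rate 0.78, one-sided alpha 0.025, exact binomial test, 114 evaluable and 126 enrolled. The number k of treated women later found ineligible is an assumption, because 11.8.1 gives no figure. Their success rate q is also an assumption; I use 0, 0.33 and 0.66.

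**The plan's own figure.** With the null-variance Z test, n = [1.960·√(0.66·0.34) + 0.842·√(0.78·0.22)]² / 0.12² = (0.9285 + 0.3486)² / 0.0144 = 113.3, so 114, as stated. For dropout, 114·1.1 = 125.4 gives the stated 126, and 114/0.9 = 126.7 would give 127. The sample size is not at issue here.

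**Exact rejection limit.** The smallest r with P(X ≥ r | n, 0.66) ≤ 0.025:

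| n | successes needed | rate | P(X ≥ r) at 66% |
|---|---|---|---|
| 126 | 94 | 74.6% | 0.0239 |
| 125 | 94 | 75.2% | 0.0171 |
| 124 | 93 | 75.0% | 0.0197 |
| 123 | 92 | 74.8% | 0.0228 |
| 122 | 92 | 75.4% | 0.0161 |
| 121 | 91 | 75.2% | 0.0187 |

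**How few women change the result.**
- 93/126 gives p = 0.0374 (fails). With two failures set aside, 93/124 gives p = 0.0197 (passes).
- 92/126 gives p = 0.0564 (fails). With three set aside, 92/123 gives p = 0.0228 (passes).

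**False-pass rate.** Hold the true rate over all 126 treated women at 66% and remove k women whose success rate is q. The remaining 126 − k then have rate p_e = (126·0.66 − k·q)/(126 − k), and the false-pass rate is P(X ≥ r | 126 − k, p_e). Example with k = 3, q = 0: p_e = 83.16/123 = 0.676 and P(X ≥ 92 | 123, 0.676) = 0.052.

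| k removed | q = 0 | q = 0.33 | q = 0.66 |
|---|---|---|---|
| 0 | 2.4% | 2.4% | 2.4% |
| 1 | 2.3% | 2.0% | 1.7% |
| 2 | 3.5% | 2.6% | 2.0% |
| 3 | 5.2% | 3.5% | 2.3% |
| 4 | 5.0% | 2.9% | 1.6% |
| 5 | 7.3% | 3.8% | 1.9% |

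The rates do not rise steadily with k because the exact limit moves in whole patients.

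**Safety.** One related SAE among 126 is 0.79% (exact 95% CI 0.02% to 4.34%). If that woman is outside the cohort, the rate is 0/125 (upper limit 2.91%). Section 9.2 expects a rate below 1%.

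**The case against.** The strongest reply is that these women are already in. Section 11.8.1 itself calls them enrolled, and 17.1.1 starts from all enrolled patients. Section 12.4.1 treats a patient as enrolled once final eligibility is confirmed, 11.9 requires that confirmation before the procedure begins, and footnote 16 of the Schedule of Events judges eligibility at that time. Nothing provides for un-enrolling a treated woman. This reading is reasonable and may be what was intended. It does not settle the matter: 17.1.1 asks whether the criteria were met, not whether they were judged to be met, and the retention sentence given for loss to follow-up is absent from the late-exclusion bullet. For the same reason, a reader who infers that these women's failures and SAEs do drop out goes further than the documents, since no passage says that they are removed.

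A reader might also infer that late-found exclusions are mostly failures, for example adenomyosis or a submucosal myoma seen at later surgery. Exclusions 4 and 20 turn largely on assessment before treatment, so a later finding need not mean that the criterion was met at enrollment. The documents give no data on how such women fare. Removal would take out successes as well, and the q = 0 column is a worst case.

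On safety, Section 6.1 says of the one commercial bowel injury that "This event was attributed to procedural use errors and the patient was not an optimal candidate for the procedure". It is tempting to read this as a case that the rule would hide, but the text does not say that she met any exclusion criterion. The primary safety endpoint has no pass/fail threshold, the CEC adjudicates events, and 17.5 tabulates all reported events.

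Finally, the regulator's letter quoted in Section 6 also describes its population as having satisfied the eligibility criteria, so the clause has a precedent. That population nevertheless counted women with exclusionary pathology found just before ablation, so the precedent does not support removing treated women.

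**Conclusion.** The conflict is real and no passage resolves it. It bears on the primary denominator, and two women set aside can be enough to turn a failed result into a pass (93/126 against 93/124).

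Whether the type I error is inflated depends on two quantities that the documents do not give. For k = 1 to 5 the false-pass rate runs from 2.3% to 7.3% if every removed woman is a failure and from 2.0% to 3.8% if such women succeed at 33%. With k = 1, or with women who do as well as the rest, it stays at or below the 2.4% obtained when all 126 are counted. These figures show what the wording permits, not what is likely.

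For safety the consequence is one of reporting: an SAE could leave the primary rate (0.8% to 0%) while remaining in the 17.5 tables. The point rests on the ambiguity in the text and does not require any intention to exclude.

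**What to change.** In 17.1.1, define ITT as all patients in whom the Minitouch procedure is initiated, whether or not an eligibility criterion is later found not to have been met. Delete the word 'qualified' from the treated-enrolled definition in 11.9 and Table 4-1. State that this cohort is used for both primary analyses, and handle eligibility deviations only in the PP cohort or a sensitivity analysis. Adding to the late-exclusion bullet in 11.8.1 the same kind of ITT sentence that the loss-to-follow-up bullet has would bring the sections into line. The change should be made before 12-month outcomes are reviewed.

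The cost is a few words and no additional patients. The reported success rate may be slightly less favourable. Counting all 126, the test needs 94 successes, with exact power of 84.8% at the planned 78%.

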17.1.2 Per Protocol (PP) Cohort

This cohort consists of all ITT Patients who are considered treatable patients, completed ablation therapy and attended 12-month follow-up visit.

The PP cohort will be used for the following analyses:

- Safety and efficacy outcome measures at 12, 24, and 36-month follow-up visits
- Secondary Analyses to assess amenorrhea rates, improvement of quality of life, evaluate patient and user (investigator) satisfaction.
- Subgroup Analyses
- Exploratory Analyses

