"Since 1997, the United States Food and Drug Administration (FDA) has approved five non-hysteroscopic global endometrial ablation (GEA) devices based on the results of randomized controlled trials (RCTs) that compared the safety and effectiveness of the GEA device to the same control – hysteroscopic rollerball ablation. Rollerball ablation is an older, well-known surgical technique used to treat heavy menstrual bleeding from benign causes. The study designs that supported the approval of the five GEA devices were very similar. They enrolled between 250 and 350 subjects using either a 1:1 or 2:1 (device: control) randomization scheme and had comparable patient populations. The primary endpoint for all five studies was the reduction in menstrual blood loss measured by the Pictorial Blood Loss Assessment Chart (PBLAC), a validated menstrual blood loss scoring system. One of the inclusion criteria required a baseline PBLAC score of at least 150 or 185, and the individual patient success criteria for effectiveness was defined as a PBLAC score of less than or equal to 75 at one year following the ablation procedure. For all subjects, pretreatment evaluation was performed to confirm the study eligibility criteria were satisfied (e.g., absence of cavity distortions, lesions that might interfere with the GEA therapy). The analysis population consisted of all subjects who presented for their scheduled treatment, having satisfied the study eligibility criteria (intent-to-treat). This analysis population included women who presented for treatment, but did not receive the planned therapy due to reasons such as identification of exclusionary pathology immediately prior to ablation, withdrawal of consent, etc. Patients with missing PBLAC scores at one year following the ablation procedures were considered treatment failures. A study was considered a success if the proportion of successes in the GEA group met a pre-specified non-inferiority margin compared to the proportion of successes in the rollerball ablation control group.

Using a generalized linear mixed model with study as a random effect, the FDA determined that the average success rate across the five GEA devices was 75.6% (65.6%, 83.5%) and 77.2% (66.5%, 85.2%) for the rollerball ablation control. The FDA performed

Page 19 of 65

CONFIDENTIAL & PROPRIETARY

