11.8 Patient Discontinuation and Replacement

Patients are free to terminate their participation (with or without reason) in the study at any time. Likewise, a patient may be terminated from the study by the investigator or the Sponsor, MicroCube, at any time if either investigator or Sponsor determines that it is not in the patient's best interest to continue participation. Enrolled patients that are terminated because of lack of compliance to protocol will not be replaced and will be considered lost to follow-up. If a patient is terminated prior to the 12-month follow up visit, this patient will be considered a treatment failure.

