12.10 Pre-Endpoint Termination Visit

If a patient terminates from the study prior to the 12-month endpoint visit, collect as much as possible of the testing below.

- 1. Serious Adverse Event collection
- 2. Concomitant Medications / Treatments
- 3. PBLAC diary collection
- 4. Menorrhagia Impact Questionnaire (MIQ)
- 5. Dysmenorrhea-related pain (NRS)
- 6. Patient Global Evaluation
- 7. Investigator Global Evaluation
- 8. Assessment of Adverse Events / Serious Adverse Events

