17.2 Analysis of Primary Efficacy Endpoint at 12-month

The primary efficacy endpoint is binary (success/failure). Success is defined as PBLAC score of \leq 75 at the 12-month follow-up assessment without incidence of additional interventions or treatments for bleeding prior to the 12-month follow-up visit. The proposed study's primary hypothesis is:

Null Hypothesis (H₀) = $p_{minitouch} \le OPC$

Alternate Hypothesis (H₁) = p_{minitouch} > OPC

where p_{minitouch} is the Minitouch Endometrial Ablation System success rate and OPC is 66% which is the FDA identified objective performance criterion (OPC) for global endometrial ablation (GEA) devices.

The exact binomial test will be conducted to compare the investigational device success rate to OPC minimum success rate for effectiveness. To achieve study success the measured success rate should exceed the 66% OPC.

ITT with imputation will be utilized to test the primary hypothesis, such that all missing data are failures for the primary endpoint. The following imputation techniques will be conducted for sensitivity analysis:

- Multiple Imputation (MI) using fully conditional specification (FCS) method, in which logistic regression is used to predict whether the missing value is likely to be a success or failure. The number of imputations will depend on the fraction of missing information.
- Tipping point, in which the numbers of successes or failures amongst missing data necessary to meet the primary endpoint hypothesis are determined.

Fisher-Freeman-Halton test will be conducted to compare the success rates between investigational sites. Results will also be stratified and compared across relevant baseline characteristics including demographics.

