17.7 Subgroup Analyses

The following subgroup analyses will be performed for both treatment success (reduction of menstrual blood loss) and amenorrhea rates for the following timepoints during study follow-up: 12, 24, and 36-months post procedure.

- Age (<40 years vs. >40 years)
- Active bleeding at the time of the operative visit (Yes vs. No)

- Transverse or low segment C-section (Yes vs. No)
- Anesthesia regimen (None vs. Sedation vs. Local Anesthesia vs. General Anesthesia vs. Multiple)
- Use environment (Office vs. Non-office)
- Uterine sound depth (6-9.0cm vs. 9.1-12cm and 6-8.0cm vs. 8.1-10cm vs. 10.1-12cm)
- Presence of anemia at Baseline defined as hemoglobin < 12 g/dL (Yes vs. No)
- Presence of fibroids at Baseline (Yes vs. No)
- Presence of ovarian cysts at Baseline (Yes vs. No)
- Presence of any intrauterine pathology at baseline (Yes vs. No)
- Contraceptive use (hormonal method vs. non-hormonal method)
- COVID-19 Status (diagnosed with COVID-19 vs. did not have COVID-19)
- COVID-19 Vaccination Status (vaccinated vs. not vaccinated)

The study is not powered for these subgroups, and therefore, there will be no hypothesis testing for the primary endpoints within these groups. These analyses will be done using the PP population.

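### The Section 17.7 subgroup success rates, and the amenorrhea, quality-of-life and satisfaction tables, are assigned to a per-protocol cohort that leaves out women the plan elsewhere counts as failures

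*Combined protocol and SAP*

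**What the plan says.** Section 17.1.2 restricts PP by what happens during and after treatment: "This cohort consists of all ITT Patients who are considered treatable patients, completed ablation therapy and attended 12-month follow-up visit". It then lists the analyses that use PP, among them "Secondary Analyses to assess amenorrhea rates, improvement of quality of life, evaluate patient and user (investigator) satisfaction", the subgroup analyses and the exploratory analyses. Section 17.7 covers treatment success and amenorrhea at 12, 24 and 36 months and confirms the population: "These analyses will be done using the PP population".

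Other sections treat women who do not reach month 12 differently:

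- Section 11.8: "If a patient is terminated prior to the 12-month follow up visit, this patient will be considered a treatment failure".
- Section 17.2: "ITT with imputation will be utilized to test the primary hypothesis, such that all missing data are failures for the primary endpoint".
- Section 6, quoting the FDA letter on the studies behind the OPC: "Patients with missing PBLAC scores at one year following the ablation procedures were considered treatment failures".
- Section 11.8.1, for women lost to follow-up: "The data from this patient is still eligible for the intent-to-treat dataset". The same section lets a woman who is contacted again resume visits at the next time point.
- Section 12.10: "If a patient terminates from the study prior to the 12-month endpoint visit, collect as much as possible of the testing below". Its list includes the PBLAC diary, MIQ, dysmenorrhea NRS and both global evaluations.

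Section 17.1.1 gives ITT the primary analyses and the 24- and 36-month safety and effectiveness analyses, by reference to Sections 9.1 and 9.2. It does not mention the secondary outcomes in Section 9.3.

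**The concern.** Completing the ablation and attending month 12 are both events after treatment has started. A table limited to women who meet those conditions describes a selected group, and the plan names no ITT counterpart for the outcomes listed above.

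Two things are at stake, both in reporting. First, treatment success would appear in one report on two bases: all treated women with missing counted as failure for the primary result, and attenders only for the subgroups. The subgroup counts would not add up to the primary result, and a reader could not tell how much of any difference is due to the rule. Second, some data that sites are asked to collect would not enter the assigned tables.

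**Working it through.** **1. The passages side by side.** A woman terminated before the month-12 visit cannot have attended it.

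| Woman | Primary analysis (17.2, 11.8) | 17.7 success rate (PP) |
|---|---|---|
| Attends month 12, PBLAC ≤ 75, no intervention | success | success |
| Attends month 12, PBLAC > 75 or earlier intervention | failure | failure |
| Terminated before month 12 | failure | not counted |
| Ablation started but not completed | in ITT | not counted |

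Early re-intervention does not by itself remove a woman from PP. Non-attendance, incomplete ablation or being judged not treatable does.

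**2. Data outside the assigned tables.** These are the 6-month PGE, IGE, MIQ and NRS of women who later miss month 12; their Section 12.10 exit assessments; and the month-24 and month-36 data of women who return after missing month 12.

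**3. The plan's own sample size (Section 17.2.1).** Inputs: null rate 66%, expected rate 78%, one-sided alpha 0.025, power 80%, normal approximation with null variance.

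n = [(1.960·√(0.66·0.34) + 0.842·√(0.78·0.22)) / 0.12]² = 113.26, rounded up to 114, as stated. For dropout, 114 × 1.10 = 125.4, rounded up to 126 as stated; 114 / 0.90 = 126.7 would round to 127. The plan's own pair, 126 and 114, implies 12 women lost (12/126 = 9.5%).

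**4. Size of the difference at month 12.** Assume the 12 have no month-12 PBLAC and are the only women outside PP. Section 17.2.1 does not say whether 78% refers to attenders or to all enrolled, so both are shown.

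- 78% among attenders: 0.78 × 114 = 88.9, so 89 successes. PP 89/114 = 78.1%; primary rule 89/126 = 70.6%; gap 7.4 points.
- 78% among all enrolled: 0.78 × 126 = 98.3, so 98 successes. PP 98/114 = 86.0%; primary rule 98/126 = 77.8%; gap 8.2 points.

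Other numbers outside PP (assumptions): with 6, the gap is 94/120 − 94/126 = 3.7 or 98/120 − 98/126 = 3.9 points. With 19, it is 83/107 − 83/126 = 11.7 or 98/107 − 98/126 = 13.8 points.

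**5. Is the gap a bias?** Take 89/114 in PP and let a share f of the 12 absent women truly succeed. The rate in all 126 is (89 + 12f)/126.

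- f = 0.5: 95/126 = 75.4%, so PP is 2.7 points higher.
- f = 0.78: about 78.1%, no difference.
- f = 1: 101/126 = 80.2%, so PP is 2.1 points lower.

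The 7.4 points therefore measure the missing-as-failure rule. The documents do not settle the sign of any true bias.

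**6. Subgroups (assumption).** Take two subgroups of 63 with 3 and 10 absent, and 78% success among attenders in both. PP shows 78% against 78%. The primary rule shows 0.78·60/63 = 74.3% against 0.78·53/63 = 65.6%. Each display hides something: PP hides the unequal loss, and the primary rule turns it into a difference in success.

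**The case against.** The strongest reply is that nothing decided by the trial depends on this. Sections 17.6 and 17.7 make the secondary and subgroup results descriptive and untested, the population is named openly, and no subgroup rate is compared with the OPC. That stands, and it is why the point is minor.

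Section 17.2 also promises primary results stratified by baseline characteristics, most naturally on ITT, and Section 17 presents itself as an outline of an SAP. ITT subgroup results may therefore be intended. But Section 17.2 names no variables beyond demographics, and it does not alter the population that Section 17.7 states.

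For month-12 MIQ, NRS, PGE and IGE, women who do not attend generally have nothing to contribute, so an available-data ITT table would be nearly the same as PP. This stands. The loss lies in the 6-month, exit and returning-visit data.

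Exclusions may also be fewer, or matter less, than illustrated. Section 12.1 accepts telemedicine visits as attendance, Section 13.11.2 allows diaries to be mailed or scanned, and Section 12.8 seeks the diary even when the visit is missed. Any of these would shrink the gap.

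Finally, missing-as-failure can create subgroup differences from dropout alone, as step 6 shows. That is a reason to show the observed-case rate beside it, not to leave the women out.

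**Conclusion.** The point holds as a minor reporting defect. Followed as written, the plan reports 17.7 success on a denominator and missing-data rule that do not reconcile with the primary analysis, and it leaves some 6-month, exit and later data out of the assigned tables. The illustrated difference is 7.4 to 8.2 points, given 12 women lost, no month-12 PBLAC for them and no other exclusions from PP. No figure can be given for amenorrhea, MIQ, NRS or satisfaction.

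A reader might infer three stronger things that the documents do not support:

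- **That PP overstates effectiveness by about 8 points.** The gap is produced by the imputation rule; against true outcomes the difference could be positive, zero or negative.
- **That the trial's conclusion is at risk.** Primary effectiveness and safety are on ITT, and ITT is also named for effectiveness at months 24 and 36.
- **That Section 11.8.1 places every early exit's data in the ITT dataset.** That sentence sits under loss to follow-up and covers only those women.

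**What to change.** In Sections 17.1 and 17.7, make ITT the leading cohort for the subgroup and secondary tables and keep PP as supportive.

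- **17.7 success at month 12:** apply the primary rule (missing or intervened counts as failure). Show the number missing and the observed-case rate in each subgroup, so that differences due to dropout alone are visible.
- **17.7 at months 24 and 36:** keep women already classed as failures under Sections 9.3 and 11.8 as failures, and show the number missing among the rest. Available data alone would drop known failures who do not attend.
- **Amenorrhea, MIQ, NRS, PGE and IGE:** use all available ITT data at each visit, with denominators, and report exit-visit data alongside.

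The cost is SAP wording and a rerun of the same tables, with no new data collection. Some descriptive rates may look less favourable.
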